#### 7.3 Collection of baseline data

After taking consent, the following demographic and clinical information and outcome measures will be obtained (Visit 0):

#### Demographic data and medical history (Visit 0)

The study team will collect the following demographic and medical history data and record it in the CRF: date of birth, age, gender, ethnic background, socioeconomic status (derived from postcode), smoking status, alcohol status, employment status and associated details of their bariatric surgery procedure, any relevant history of disease, prescribed and concomitant medications, or any other relevant surgical interventions.

## Physical examination (Visit 0)

The following anthropometric measures will be obtained: Height (cm), Waist circumference (cm), body Mass (kg) body mass index (kg.m²). Systolic and diastolic blood pressure (mmHg) and resting heart rate (bpm) will be recorded after the participant has been seated for at least five minutes. An accelerometer will be fitted ahead of the maximal exercise test.

#### Screening blood tests (Visit 0)

Blood tests for screening for diabetes (HbA1C), haemoglobin levels (Full blood count, FBC), kidney (U+Es and eGFR) and liver function (LFTs) will be performed at visit 0. All blood tests performed during the study will be reviewed and the reports signed by the Investigator (or an individual/individuals approved by the CI as listed on the delegation of authority log) who will record in the CRF whether they are normal, abnormal but not clinically significant, or abnormal. If abnormal a letter will be sent to the GP.

#### Estimation of Daily Energy Requirements (Visit 0)

The daily energy requirements for each participant (for provision of the standardised meals to participants during the treatment periods in accordance with their daily energy requirements) will be estimated using the Mifflin-St Jeor equation (MSJE) which uses height, weight and age to calculate resting energy expenditure. The activity factor will depend on level of activity categorised as sedentary, lightly active, moderately active, very active and extra active.

#### Maximal exercise test and ECG (Visit 0)

The supervised maximal exercise test is a reliable measurement of physical capacity and aerobic fitness (33, 34), with a 12 lead electrocardiogram, blood pressure monitoring and other associated measures. The test will be used as a screening measure in order to ensure that participants are safe to participate in exercise and to determine their maximum aerobic capacity (VO2peak) which will inform the exercise level performed on visits 2 or 4. This incremental walking test will identify potential contraindications to exercise and will assess the suitability to participate to the study. The supervised maximal exercise test report will be signed by the delegated investigator who will record in the CRF whether it is normal, abnormal but not clinically significant, or abnormal AND clinically

significant. Referrals to the appropriate healthcare professional, i.e. cardiology or the participants' general practitioner (GP) will be made in any such case. The participant may be retained and reevaluated if no issues of concern emerge; otherwise, the participant will be withdrawn. A blood glucose meter and training on capillary blood glucose (CBG) testing and HYPO treatment in case of symptomatic HYPO will be provided to all participants after the maximal exercise test at visit 0 (for safety purposes).

A graded treadmill maximal exercise test will be undertaken at a fixed speed (as determined by participant ability) with progressively increasing gradient, according to SOPs developed within the NIHR Leicester Biomedical Research Centre. The test includes participant pre-screening involving medical history review by an appropriately trained member of the study team and resting electrocardiography (ECG).

After an opportunity to familiarise themselves with the treadmill, participants will complete a 3-5 minute warm up at a light intensity (speed  $\leq$ 4km/h). Participants will then walk at the fixed speed at a 0% gradient, before the gradient increases by 1% each minute for the duration of the test. A walking speed of less than 4km/h will be selected where participants are unable to comfortably walk at this pace without incline. Participants will be encouraged to continue the test until (a) volitional exhaustion, (b) participants reached 100% of their age-predicted maximum heart rate (85% if taking  $\beta$ -blockers) and a Respiratory Exchange Ratio (RER) of  $\geq$  1.15 or (c) the test is terminated by the cardiac nurse/clinician, who will monitor the entire test using a 12-lead ECG. The latter will be classified as an incomplete test. In the instance where cardiac nurse/clinician suspects a cardiac abnormality and terminates the test, the participant will be referred for further investigation

An appropriately trained member of staff will assess heart rate and collect expired air that will be processed through an automated breath-by-breath analyser. Rating of perceived exertion (RPE) (rating 6-20) will also be recorded regularly throughout the test. A rolling average of 10 breaths will be calculated for  $\dot{V}O_2$  and  $\dot{V}CO_2$ , and peak oxygen uptake ( $\dot{V}O_{2peak}$ ) will be defined at the highest number. The RER and heart rate at  $\dot{V}O_{2peak}$  will also be reported.

#### 7.4 Primary outcome measure

Continuous glucose monitoring (CGM) (Dexcom G6) (Visits 1 and 3)

CGM is a minimally invasive technique used for monitoring interstitial blood glucose levels. A commercially available glucose sensor (Dexcom G6) is inserted into the abdominal subcutaneous tissue (5mm depth) and measures glucose levels at this site continuously for up to 10 consecutive days (duration of life of a sensor). It provides an average blood glucose reading every five minutes and is suitable for use during normal everyday activities including bathing and most physical activities. The device does not require calibration with CBG monitoring, however the CGM receiver should be within a 6 metre distance of the CGM transmitter in order to capture all CGM recordings. We anticipate obtaining more than 20h of stable recording over the 24h period of monitoring post-intervention for each treatment period (primary outcome). The CGM data will be blinded to ensure patients' diet habits are not affected by monitoring of glucose levels. When the device is detached, the software uploads time stamped data in an excel format.

At visit 1 the blinded CGM device (Dexcom G6) will be fitted to participants and a glucose monitoring diary provided to monitor throughout the treatment period timeframes. Full training in CBG testing in case of HYPO symptoms and education on HYPO treatment will be provided to all participants at visit 0 with education reminders at visits 1 and 3, before returning home. Participants will use the same blinded CGM device throughout the study period. However, if there are issues regarding sensor life (for example if the end of the second treatment period is more than 10 days from Dexcom G6 sensor insertion), a new CGM sensor will be issued at visit 3 where necessary, together with a new glucose monitoring diary.

#### 7.5 Secondary outcome measures

#### Blood samples for insulin, glucose and appetite biomarkers

Blood sample collection (insulin, glucose and biomarkers of appetite) throughout the experimental period and during lunch time mixed meal tolerance test (MMTT) will be undertaken. The MMTT will be performed 45mins after completion of AEX and at a similar point in the control condition) (Visits 2 and 4).

Glucose will be measured at 11 time points throughout the duration of each experimental period using cannulation of the participant's forearm. The blood samples will be collected at the following time points: when the participant arrives in a fasted condition, immediately before the intervention (+2h 15min), immediately after the end of the intervention (+2h 50min), immediately before the MMTT at lunchtime (+3h 30min) and then after completion of lunch at 15 minutes, 30 minutes, 60

minutes, 90 minutes, 120 minutes, 150 minutes, and 180 minutes. Consumption of the standardised MMTT at lunchtime will be completed within 15 minutes (extra 5 minutes will be given to complete meal consumption if needed). A total of 88ml of blood (approximately 8ml per sample) will be collected for insulin and glucose.

An optional extra amount of approximately 7 mls per sampling (overall additional 77 mls of blood) will be collected for sample storing for future analysis of appetite biomarkers (if consent has been obtained). These samples will be analysed in a specialised lab based at Loughborough University. Blood for glucose levels will be collected into Fluoride/Oxalate tubes. Glucose samples will be measured using standardised quality-controlled assays at the University Hospitals of Leicester NHS trust.

Blood for measurement of insulin will be assessed in fasting condition, pre-MMTT (i.e., immediately before the standardised MMTT at lunchtime) and then starting from the 'time of the last mouthful of the meal' at 15 minutes, 30 minutes, 60 minutes, 90 minutes, 120 minutes, 150 minutes, and 180 minutes post-meal to correspond with the glucose measurements.

Blood samples for insulin will be collected into pre-cooled blood collection tubes containing EDTA (EDTA 4.9 ml, 1 tube at each time point) to ensure sample viability for hormone/metabolite biochemical analysis. Blood collection tubes for insulin will be kept on ice prior to their use.

Blood samples for majority of appetite biomarkers will be collected into pre-cooled blood collection tubes pre-treated with 250ul of aprotinin (EDTA 4.9ml, 1 tube at each time point) at the same time points that blood sampling for insulin and glucose takes place. At the same time points, 2ml of blood will be collected with syringe and will be processed in accordance with the Leicester Diabetes Centre standard operating procedures for blood collection for measurement of acylated ghrelin, a hunger hormone.

#### Hypoglycaemia (HYPO) during the MMTT

This will be defined as plasma glucose ≤3.0mmol/l during the 3-h MMTT (please see section 9.4 for definitions of HYPO during MMTT).

It is noted that decisions regarding treatment of HYPO during the MMTT will be made in accordance with venous blood glucose/capillary blood glucose values and symptoms of the patient (instead of plasma glucose levels which will be performed at the UHL lab). More specifically if the participant experiences symptoms suggestive of HYPO and venous blood glucose/capillary blood glucose levels

are ≤3.0mmol/l, the participant will receive treatment for HYPO in accordance with HYPO Guideline for Adults of the UHL. The blood collection for measurement of insulin, glucose and appetite biomarkers as well as the VAS score collection for hunger and satiety during the MMTT will be terminated. The participant will remain in sitting position after HYPO treatment until the expected time of completion of the experimental period (≈+6h 45min). It is not expected that patients will experience severe hypoglycaemia during the study as patients will be excluded at screening if they report frequent and severe symptoms of postprandial hypoglycaemia during daily life or they have an established diagnosis of PHH after bariatric surgery.

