The AEX session will be supervised by an appropriately trained member of the study team and conducted on a treadmill, at the same brisk walking speed self-selected during the maximal exercise test, at a gradient predicted to elicit 60% of each participant's VO2 peak based on the screening assessment. The duration of the AEX session will be 30 min. This bout of AEX will be preceded by a 3-min warm up and followed by a 2-min cool down, such that the total bout will be 35 min. Blood pressure will be recorded before and after exercise and heart rate and rating of perceived exercise (RPE) will be recorded throughout. Participants will remain rested and seated throughout the control condition.

The participant will be provided a second meal (mixed meal tolerance test (MMTT)) approximately +3h 30min into the trial visit, comprising 30% of estimated energy requirements. The food items provided will be guided by participant preferences obtained at Visit 0. Meals consumed at Visit 2 will be replicated at Visit 4.

The MMTT will be consumed over 15min (extra 5 minutes will be given to complete meal consumption if needed) at visit 2 and 4. Blood samples (8 ml per sampling) for measurement of glucose homeostasis' parameters (glucose, insulin) will be collected at 11 time-points, through the inserted cannula, immediately before the meal (+3h 30min) and then 15min, 30min, 60min, 90min, 120min, 150min, 180min after lunch consumption. At the same time points additional blood sample of approximately 7ml per sampling will be taken for storage of plasma for future measurement of biomarkers of appetite (appetite hormones). Visual analogue scale (VAS) scores for hunger and satiety will be completed at each time point of blood sampling (30) (Appendix 2). After completion of the 3-h blood sampling period post-MMTT at lunchtime (≈+6h 45min, ~16:00), participants will be free to go home and resume their normal daily activities (see below for more detail).

Throughout the visit the study clinical team will monitor the participants for HYPO and the participants will also be asked to report any signs or symptoms suggestive of HYPO. If participants experience symptoms suggestive of HYPO, capillary/venous blood glucose will be measured at bedside through a glucose meter for safety purposes. Only symptomatic hypoglycaemia will be treated during the experimental period (visit 2). At the onset of a symptomatic HYPO (defined as

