capillary/venous blood glucose <3.0 mmol/l with symptoms suggestive of HYPO), treatment will be provided in accordance with the University Hospitals of Leicester Hypoglycaemia Guideline.

If symptomatic HYPO takes place after completion of the intervention but before the initiation of the MMTT at lunchtime, then the HYPO will be treated and the standardised MMTT will take place but without sample collection for plasma glucose, insulin and biomarkers of appetite and VAS score for hunger and satiety. The participant will remain at sitting position after treatment of HYPO until the end of the experimental period at ≈+6h 45min. If symptomatic HYPO takes place after initiation of the MMTT at lunchtime, HYPO will be treated and the sample collection for plasma glucose, insulin and biomarkers of appetite as well as the VAS score for hunger and satiety will be terminated after treatment of HYPO. However, participant will remain at sitting position after treatment of HYPO until the end of the experimental period at ≈+6h 45min.

If symptomatic HYPO takes place before completion of the intervention, this will mean termination of the experimental period. The participant will be given the option to re-arrange this appointment in case of symptomatic hypoglycaemia before the completion of the intervention.

All participants' habitual physical activity will be assessed using a wrist-worn accelerometer. Participants will be asked to test their CBG levels only if they experience HYPO symptoms and to treat HYPO only if CBG <3.0mmol/l. It is expected that 80% of HYPO episodes will be asymptomatic (8).

Participants will be provided with a standardised evening meal to take and consume at a set time at home, as well as with a standardised breakfast and lunch for the following day (day 3 of each investigational period) to be consumed at set times.

Participants will be asked to keep a 3-day diet diary, glucose monitoring diary and a wake and sleep log until 24-h after the end of the intervention. Participants will also be encouraged, but this will not be obligatory, to continue keeping a glucose monitoring diary and wake and sleep log during the washout period of the study (between the 1st and 2nd treatment period), as they will continue to wear an accelerometer and the continuous glucose monitoring device (until at least the end of sensor's life for the CGM device).

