## Secondary outcomes:

- 1. Difference in Area Under the Curve (AUC)(0-180), pre-meal, peak and nadir glucose levels after mixed meal tolerance test (3-h MMTT) between the two interventions (AEX vs control) after bariatric surgery (RYGB and SG).
- 2. Difference in  $AUC_{(0-180)}$  insulin, pre-meal and peak insulin levels during the 3-h MMTT between the two interventions (AEX vs control) after bariatric surgery (RYGB and SG).
- 3. Difference in the ratio  $AUC_{(0-180)}$  insulin/ $AUC_{(0-180)}$  glucose during the 3-h MMTT between the two interventions (AEX vs control) after bariatric surgery (RYGB and SG).
- 4. Difference in the ratio  $AUC_{(0-30)}$  insulin/ $AUC_{(0-30)}$  glucose during the 3-h MMTT between the two interventions (AEX vs control) after bariatric surgery (RYGB and SG).
- 5. Difference in the ratio  $AUC_{(60-180)}$  insulin/ $AUC_{(60-180)}$  glucose during the 3-h MMTT between the two interventions (AEX vs control) after bariatric surgery (RYGB and SG).
- 6. Difference in the ratio of maximum/minimum plasma glucose during the 3-h MMTT between the two interventions (AEX vs control) after bariatric surgery (RYGB and SG).
- 7. Difference at the number of mixed meal tests required to be stopped due to symptomatic HYPO with blood glucose/capillary glucose levels <3.0 mmol/l during the 3-h MMTT between the two interventions (AEX vs control) after bariatric surgery (RYGB and SG).
- 8. Difference in %time in interstitial glucose levels <3.9 mmol/l in CGM between the two interventions (AEX vs control) after bariatric surgery (RYGB and SG) during the 24-h period after completion of the intervention.
- 9. Difference in %time in interstitial glucose levels <3.3 mmol/l in CGM between the two interventions (AEX vs control) after bariatric surgery (RYGB and SG) during the 24-h period after completion of the intervention.
- 10. Difference in % time in interstitial glucose levels <2.2 mmol/l in CGM between the two interventions (AEX vs control) after bariatric surgery (RYGB and SG) during the 24-h period after completion of the intervention.

- 11. Difference in % time in range (definition 1, defined as interstitial glucose levels between 3.9 7.8 mmol/l) in CGM between the two interventions (AEX vs control) after bariatric surgery (RYGB and SG) during the 24-h period after completion of the intervention.

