#### Definition of hypoglycaemia during the mixed meal tolerance test (MMTT)

Asymptomatic hypoglycaemia during the MMTT will be defined as plasma glucose <3.0 mmol/l not accompanied with typical symptoms of hypoglycaemia.

Symptomatic hypoglycaemia during the MMTT will be defined as plasma glucose <3.0 mmol/l accompanied with typical symptoms of hypoglycaemia.

Relative hypoglycaemia during MMTT will be defined as an episode during which the participant reports any of the typical symptoms of hypoglycaemia and interprets, but plasma glucose levels are ≥3.0 mmol/L.

It is noted that decisions regarding treatment of hypoglycaemia during the MMTT will be made in accordance with venous blood glucose/capillary blood glucose values and symptoms of the patient (instead of plasma glucose levels which will be performed at the UHL lab). More specifically if the participant experiences symptoms suggestive of hypoglycaemia and venous blood glucose/capillary blood glucose levels are <3.0mmol/l, then the participant will receive treatment for HYPO in accordance with HYPO Guideline for Adults of the UHL and the blood collection for measurement of insulin, glucose and appetite biomarkers as well as the VAS score collection for hunger and satiety during the MMTT will be terminated. The participant will remain in sitting position after HYPO treatment until the expected time of completion of the experimental period. It is noted that it is not expected that patients will experience severe hypoglycaemia during the study as patients will be excluded at screening if they have an established diagnosis of PHH after bariatric surgery.

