#### 11. STATISTICS

#### 11.1 Description of Statistical Methods

A CONSORT study flow diagram will detail the movement of participants throughout the BariEX study. Baseline descriptive characteristics will be summarised, with continuous variables expressed as mean values (and standard deviations) or median values (with lower and upper quartiles) where appropriate, and binary and categorical variables expressed as number (percentage). Where CGM data is missing from a given trial, the corresponding data will be excluded from the other trial during the same time period at the second treatment. Participants with less than 16-hours 48min CGM data available for analysis over the 24-hour period after the intervention will be excluded from the complete cases analysis. The primary outcome of the study will be the difference in the time spent in HYPO (defined as glucose levels <3.0 mmol/l as measured by CGM) between the AEX and control intervention during the first 24-h post-intervention.

For outcomes related to the standardized MMTT (secondary outcomes), data from blood samples collected pre-MMTT at lunchtime (exactly before MMTT consumption) and 15, 30, 60, 90, 120, 150 and 180 minutes after MMTT consumption (last mouthful of MMTT) will be used to calculate time-averaged AUC (Area Under the Curve), using the trapezium rule. In instances of symptomatic hypoglycaemia during the MMTT(where blood collection for glucose, insulin and appetite biomarkers as well as VAS scores for satiety and hunger will be terminated early), these participants will be excluded from the analysis of secondary outcomes related to the MMTT. Missing data on insulin, glucose, appetite biomarkers and VAS scores for satiety and hunger within a completed MMTT will be imputed using a linear regression method as previously reported (35, 36), provided baseline/pre meal value and ≥50% of data points within the MMTT are available. The primary and secondary outcomes will be analysed using GEE (Generalised Estimating Equations) with an exchangeable correlation matrix, taking into account repeated measures across conditions. Outcome distribution will be assessed, with Gamma models used for positively skewed data. Identity and log link functions will be explored with Gamma models, with an identity link preferred (to aid interpretation of results) unless log link provides a substantially superior model fit.

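### Section 7.5 puts the MMTT hypoglycaemia definition and treat-and-stop trigger at ≤3.0 mmol/l, sections 5.1 and 9.4 at <3.0, so a symptomatic reading of exactly 3.0 falls under conflicting rules

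*Protocol*

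**What the plan says.** Section 7.5, under the heading on hypoglycaemia during the MMTT, uses ≤3.0 mmol/l twice. The first use is the plasma definition: "This will be defined as plasma glucose ≤3.0mmol/l during the 3-h MMTT". That sentence sends the reader to section 9.4 for the definitions. The second use is the bedside rule. If a participant has symptoms and venous or capillary values "are ≤3.0mmol/l, the participant will receive treatment for HYPO in accordance with HYPO Guideline for Adults of the UHL". Blood collection then ends, "as well as the VAS score collection for hunger and satiety during the MMTT will be terminated".

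Section 9.4 repeats this bedside paragraph almost unchanged, but with the other inequality sign: "blood glucose levels are <3.0mmol/l, then the participant will receive treatment for HYPO". Its plasma definitions of symptomatic and asymptomatic hypoglycaemia in the MMTT also use <3.0, and it classes a symptomatic plasma value of 3.0 or above as relative hypoglycaemia.

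Section 5.1, in the account of visits 2 and 4, says: "Only symptomatic hypoglycaemia will be treated during the experimental period (visit 2". It defines a symptomatic episode as "capillary/venous blood glucose <3.0 mmol/l with symptoms suggestive of HYPO), treatment will be provided". If such an episode occurs once the MMTT has begun, sampling is to end after treatment.

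Secondary outcome 7 in section 5.2 compares the number of meal tests stopped because of "symptomatic HYPO with blood glucose/capillary glucose levels <3.0 mmol/l during the 3-h MMTT". Section 11.1 says what happens to tests in which collection ended early: "these participants will be excluded from the analysis of secondary outcomes related to the MMTT".

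**The concern.** The same bedside reading, in the same test, triggers the same action under two different inequalities. It decides four things: whether the participant is treated, whether the remaining samples are drawn, whether the participant stays in the MMTT analyses, and whether the test counts under outcome 7. For a symptomatic reading of exactly 3.0 mmol/l, staff cannot comply with every section.

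A statistical analysis plan could not fully repair this. The bedside rule determines which samples exist, so part of the outcome is settled before analysis begins. Outcome 7 and the exclusion in section 11.1 should describe the same set of stopped tests. As written, they need not.

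**Working it through.** The protocol gives no figure to reproduce here. The check is a side-by-side reading of every place that defines MMTT hypoglycaemia or acts on it.

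| Protocol section | Role of the threshold | Limit (mmol/l) | Symptomatic value of exactly 3.0 |
|---|---|---|---|
| 7.5 | Plasma definition | ≤3.0 | Hypoglycaemia |
| 7.5 | Bedside trigger for treatment and end of sampling | ≤3.0 | Trigger met |
| 5.1 | Bedside definition and trigger | <3.0 | Trigger not met; treatment is limited to symptomatic episodes so defined |
| 9.4 | Plasma definition | <3.0 | Relative hypoglycaemia |
| 9.4 | Bedside trigger for treatment and end of sampling | <3.0 | Trigger not met; no instruction given for this value |
| 5.2, outcome 7 | Counting of stopped tests | <3.0 | Not counted |

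Take a participant with symptoms and a bedside reading of 3.0 during the MMTT.

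1. **Staff follow 7.5.** The participant is treated and sampling stops. The later blood and VAS values do not exist. Section 11.1 excludes participants whose collection ended early, and it allows imputation only within a completed MMTT, so the gap cannot be filled. The reading is not below 3.0, so outcome 7 does not count the stop. The test is lost from the MMTT outcomes and is also missing from the outcome meant to record such losses.
2. **Staff follow 5.1 or 9.4.** The trigger is not met and nothing in those sections ends sampling. The test can run to 180 minutes and stays in the MMTT analyses. Outcome 7 does not count it, which is consistent with what happened.

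Any reading below 3.0 is handled alike by all the sections, and so is any reading above 3.0. The conflict is confined to the boundary value.

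**Scale of one such case.** Section 11.2 plans 18 participants with 20% drop-out: 18 × (1 − 0.20) = 14.4, or about 14 completers. One excluded participant is 1/14 ≈ 7% of them for every MMTT outcome. This figure is conditional on a case occurring. It is not an estimate of how often one will.

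**The case against.** The strongest reply is that the definition is largely settled, because the sentence in 7.5 points to 9.4 and 9.4 uses <3.0 throughout. That carries weight for the plasma definition, although the pointer then leads to a section that contradicts the sentence containing it. It does not help with the bedside trigger. Section 7.5 states separately that treatment decisions rest on venous or capillary values rather than laboratory plasma glucose, and it gives its own limit of ≤3.0 for them.

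The second reply is rarity. A case needs symptoms, a bedside reading of exactly 3.0 and a time within the three-hour test. Section 5.1 expects 80% of hypoglycaemic episodes to be asymptomatic, and section 6.3 excludes people with an established diagnosis of postprandial hypoglycaemia. This stands. There may be no case at all.

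Four stronger readings are tempting, and the document does not support them.

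- A reader might infer that every other section forbids treatment at 3.0. Only section 5.1 does so, by restricting treatment to symptomatic episodes as it defines them. Section 9.4 is silent on that value, and outcome 7 is a counting rule that sets no trigger.
- A reader might infer that unblinded staff would apply the two limits differently by condition. Nothing in the protocol indicates this.
- A reader might try to put a probability on a reading of 3.0. The protocol gives neither the resolution of the meter nor the distribution of readings, so any fraction would reflect a range chosen by the reader.
- A reader might infer that the primary outcome is compromised, since the MMTT falls within the 24 hours after the intervention. The CGM definition is <3.0 wherever it is stated and is not in conflict. Any effect of treating at 3.0 on later CGM values cannot be sized from the document.

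**Conclusion.** The contradiction holds, in current protocol text. Section 7.5 uses ≤3.0 mmol/l both for the MMTT definition and for the treat-and-stop trigger. Sections 5.1 and 9.4 use <3.0 for these, and outcome 7 counts at <3.0. A test stopped at exactly 3.0 under 7.5 is excluded by section 11.1 without appearing in outcome 7.

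The practical size is small and possibly nil. The conclusion that the rules conflict rests on the wording alone and needs no assumption about frequency. This is a minor correction, but more than a stray typing error, because the threshold governs a bedside action and determines which data exist. The review takes no position on which limit is right.

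**What to change.** Reconcile sections 5.1, 5.2 (outcome 7), 7.5 and 9.4 so that one threshold serves the definition, treatment, the ending of sampling and the counting of stopped tests. The clinical team should decide which threshold that is.

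Check the MMTT records already collected for tests stopped at a reading of 3.0, and report how many there were and in which condition. Do not reclassify completed tests retrospectively. A new label cannot recover samples that were never drawn, and applied in the other direction it could discard complete data, although section 11.1 aims its exclusion at tests that ended early.

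The cost is a wording amendment and a short record check. The sample size and the primary analysis do not change.
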